#### **4.1.b. Primary Purpose**

Prevention

#### **4.1.c. Interventions**

Type:

Behavioral

Name: *(up to 200 characters)*

STAC-T Parent Module

Description: *(up to 1000 characters)*

Parent-based bullying intervention

#### **4.1.d. Study Phase**

## Phase 1

Is this an NIH-defined Phase III clinical trial?

Device and behavioral intervention studies may select "Yes" here even if the answer above is "Other".

Yes  No

### 4.1.e. Intervention Model

Single Group

### 4.1.f. Masking

If yes:

Choose an item.

### 4.1.g. Allocation

N/A

## 4.2 Outcome Measures

### Type

Primary

### Name

Parent-Advocates Pre- and Post-Scale (PAPPS)

### Time Frame

Baseline assessment, immediate post-assessment

### Brief Description:

An 11-item questionnaire measuring parent knowledge of bullying, knowledge of the parent STAC strategies, and parent confidence to supporting their adolescent to intervene in bullying situations.

### Type

Primary

### Name

National Education Association Bullying Survey

### Time Frame

Baseline assessment, immediate post-assessment

### Brief Description:

This questionnaire has items that measures comfort managing bullying (4 items on a 4-point likert scale), confidence about managing bullying behavior (3 items on a 5-point likert scale), and role in managing bullying behavior (4 items on a 4-point likert scale). The questionnaire also has items related to experiences with bullying.

### Type

Primary

### Name

Parent Self-Efficacy Scale

### Time Frame

Baseline assessment, immediate post-assessment

### Brief Description:

The Parent Self-Efficacy Scale measures parent self-efficacy . A 6-item scale measures parent self-efficacy in

helping adolescents respond to bullying behavior. Items are rated on a 4-point Likert Scale. A 6-item scale measures parent communication self-efficacy in talking to adolescents about bullying. Items are rated on a 5-point Likert Scale.

**Type**

Primary

**Name**

Attitudes about Bullying Questionnaire

**Time Frame**

Baseline assessment, immediate post-assessment

**Brief Description:**

The 10-item Attitudes about Bullying Questionnaire measures parent attitudes about bullying. Items are rated on a 5-point Likert Scale.

**Type**

Primary

**Name**

Student Social Behavior Questionnaire

**Time Frame**

Baseline assessment, immediate post-assessment

**Brief Description:**

The 13-item Student Social Behavior Questionnaire measures parent attitudes about bullying. Items are rated on a 5-point Likert Scale.

**Type**

Primary

**Name**

Intention to Use Parent STAC Strategies

**Time Frame**

Immediate post-assessment

**Brief Description:**

Questions rating the parent intention use of each parent STAC strategy using a single item rated on a 5-point Likert scale: How likely are you to use these strategies to support your adolescent to intervene in bullying in the past month? (a) Stealing the Show; (b) Turning it Over; (c) Accompanying Others; and (d) Coaching Compassion.

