##### **3.1.1.2. Study Procedures:**

Three middle schools in rural, low-income communities in Idaho (N=40) will test the STAC Parent Module to evaluate program acceptability, feasibility, changes in knowledge, confidence, attitudes about bullying, and self-efficacy, and intention to use the parent STAC strategies. Outcomes of knowledge, confidence, attitudes, and self-efficacy will be tested immediately before and after the STAC Parent Module training session.

Program acceptability and intentions to use the strategies will be measures immediately after the STAC Parent Module Training. All parents of students in grades 6, 7, and 8 will be invited to participate. Recruitment will continue until sample size is met. Parents who provide informed consent will be invited to participate in the study during evening hours at a room provided by the school. Parents will be provided a unique study ID number and will complete the baseline assessment. Immediately after completing the baseline assessment (10-15 minutes), parents will participate in the STAC Parent Module training (50 minutes). Participants will then complete an immediate post-training assessment (10-15 minutes). Data collection and training will occur in person although we do have the ability to conduct sessions remotely if needed following similar procedures we have used during COVID-19. Baseline Assessment: Parents will complete a survey assessing knowledge, confidence, attitudes about bullying, self-efficacy, and demographic characteristics. Immediate-Post Assessment: Immediately following the STAC Parent Module training, parents will complete a survey assessing acceptability of the STAC Parent Module, knowledge, confidence, attitudes about bullying, self-efficacy, and intentions to use the STAC parent strategies. Parents will be randomly selected to participate in focus groups which will occur within a week post-training. In three focus groups with parents of middle school students (6-8 per group; N=12-16), participants will be asked to talk about the content of the training, as well as asked about current practices, school needs and interest in the future for a technology-based, bullying parent intervention, and challenges and barriers to use. The focus groups will be led by research staff trained in focus group moderation, encouraging open non-judgmental discussion. Focus groups will be conducted in-person

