Among middle school students, only about half of student report bullying to an adult, fearing adults will minimize or normalize bullying or make the situation worse. When students do report bullying to an adult, they most often report to parents, followed by teachers. Parents, however, are less likely to intervene in school bullying than teachers and when they do intervene, parents may not be effective. In fact, some parents suggest coping strategies that are not only ineffective, but may exacerbate the situation. Further, parents do not have a shared definition of bullying, normalize verbal and relational bullying, feel frustrated and helpless in response to bullying, are often unaware that bullying is occurring, and need information and guidance. However, few bullying interventions include parent education and the resources required for implementation of those that do pose significant barriers for schools. Although research indicates school personnel believe parental involvement in bullying intervention is important, that parents and teachers need to convey unified messages in a comprehensive, coordinated manner, and that parents need information and guidelines about bullying, involving parents in bullying prevention is a challenge for schools, particularly in rural and low-income

communities.

The overall CTR-IN pilot project goal is to develop the content for a STAC Parent Module. The project will be completed in 11.5 months and will consist of two stages: (1) content development and (2) testing of program acceptability, feasibility, and short-term outcomes. The primary outcomes are increases in knowledge and confidence, changes in bullying attitudes, increases in self-efficacy to manage bullying, and intentions to use the parent strategies. The secondary outcomes are related to program acceptability. Parents will complete baseline and immediate post-intervention assessments.

The proposed project is a first step in developing the STAC-T Parent Module. This project will provide the pilot data needed to support a NIMHD STTR/SBIR R41/42 fast-track proposal aimed at developing the STAC-T Parent Module for middle schools in rural and low-income communities. The aims of the pilot study are to:

**(1) Develop the content for the Parent Module.** Our previous research with school personnel and the bullying literature will guide the creation of the Parent Module content.

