**(2) Assess the feasibility, acceptability, and immediate outcomes (e.g., knowledge, attitudes, self-efficacy, and behavioral intentions) of the STAC-T Parent Module.** We will conduct a mixed-methods study with parents ( $N = 40$ ) from two middle schools, assessing program acceptability and post-training outcomes through survey data; a subgroup of parents ( $N = 12-16$ ) will participate in focus groups, providing feedback about content, feasibility, and acceptability of the Parent Module for schools in rural, low-income communities.

A mixed-methods approach will be utilized; 40 parents will be recruited from three public middle school located in rural, low-income communities in Idaho. All parents of students in 6th- 8th grade meeting inclusion/exclusion criteria will be recruited through e-flyers and email reminders sent by the school and asked to sign up to participate. We will continue recruitment at each school until we reach the target sample. The e-flyer will explain the study and include a survey link to sign up for participation, as well as a project phone number and email address. Parents will be invited to participate in the study in the evening at the school. Parents who provide consent will be provided a unique study ID number and will complete the baseline assessment. Immediately after completing the baseline assessment, parents will complete the Parent Module training. Following the training, parents will complete the follow-up assessment. Baseline assessments include a survey assessing knowledge, confidence, attitudes, self-efficacy, and demographic characteristics. Immediately following the STAC Parent training, parents will complete a survey assessing acceptability of the training, knowledge, confidence, attitudes, self-efficacy, and behavioral intentions to use the STAC parent strategies.

Study consents and assessments will be collected via paper-pencil format. All data will be input into SPSS; data will be de-identified and stored in Boise State's secured database. Boise State's protocols for quality assurance (valid ranges; internal consistency checks, etc.) will ensure high quality data.

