### 4.3 Statistical Analysis Plan

Analyses will be conducted on data collected. While unlikely, data may not be missing at random (NMAR). [name], Project Biostatistician, will assign all lost responses to extreme category and perform multiple imputation procedures that can handle various amounts of missing data and use covariates and propensity scores.

The primary outcomes are detecting positive changes in knowledge acquisition and confidence, attitudes about bullying, self-efficacy regarding bullying, and intention to use of the STAC parent strategies. The secondary outcomes are program acceptability. A total of 20 parents within one school provides at least 80% power to detect a difference in baseline and immediate follow-up corresponding to a medium effect size (e.g., Cohen's  $d = .5$ ) with a 5% type I error probability. For this power analysis, pilot data from a sample of teachers were analyzed using measures similar to those proposed in this study. We will use three schools to ensure ecological validity and estimate the random effect for school for powering our future proposals involving multiple schools. We propose planning for 40 parents.

Descriptive statistics will be used to initially characterize the outcomes. We will use linear or generalized linear mixed model framework, with random effects of repeated observations on parents and parents nested within school.

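### The primary intention item asks about future use over a past month, and Section 4.3 lists this post-training-only outcome among the changes to be detected

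*Combined protocol and SAP*

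**What the plan says.** Section 4.2 lists six primary measures. One is "Intention to Use Parent STAC Strategies", with time frame "Immediate post-assessment". Its brief description gives one stem, rated on a 5-point scale for each of the four STAC strategies: "How likely are you to use these strategies to support your adolescent to intervene in bullying in the past month".

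The timing is the same elsewhere. Section 3.1.1.2 states: "Program acceptability and intentions to use the strategies will be measures immediately after the STAC Parent Module Training". Section 4.1.a gives the baseline content, and intention is not in it: "Baseline assessments include a survey assessing knowledge, confidence, attitudes, self-efficacy, and demographic characteristics".

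The plan states the outcome in different ways:

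- Section 4.1.a attaches a word of increase or change to each of the other primary outcomes and leaves intention without one: "increases in self-efficacy to manage bullying, and intentions to use the parent strategies".
- Section 4.3, where the primary outcomes are defined for analysis, puts intention at the end of a list of changes: "The primary outcomes are detecting positive changes in knowledge acquisition and confidence, attitudes about bullying, self-efficacy regarding bullying, and intention to use".
- The last paragraph of Section 4.3 first separates outcomes compared between baseline and follow-up from intention, which it evaluates at follow-up only. It then says that, to find changes, every outcome will be analysed in a mixed model with random effects for repeated observations on parents and for parents within school.

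**The concern.** There are two faults, both on a primary outcome.

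The first is the item. A question about how likely someone is to do something concerns the future; a past-month window concerns the past. Asked straight after a first training session, past-month use of strategies just taught has no clear meaning. If the form carries this stem, a low rating could mean no past use or no intention to use, and the plan's only primary measure of intention could not be read clearly.

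The second is the analysis. A reader who follows the outcome definition or the model sentence in Section 4.3 literally could report a single post-training level as an improvement. The pilot is meant to support a larger proposal, so an unsupported claim of change could be carried forward.

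**Working it through.** The plan gives no figure on this point to reproduce. The power statement in Section 4.3 concerns a difference between baseline and follow-up, so it does not cover intention. The check compares the texts, counts records and asks what the stated model can estimate.

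**1. The stem against its name.** The outcome is named as intention and the verb in the stem is prospective, but the window is the month already past. The sentence is complete as printed, so this is not a gap left by text extraction. It appears in a brief description and the survey form is not in the documents. Either the form has the same stem and the item is faulty, or the form is sound and only the description is wrong.

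**2. Time points in Section 4.2.**

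| Measure | Type | Baseline | Post |
|---|---|---|---|
| Parent-Advocates scale | Primary | yes | yes |
| National Education Association survey | Primary | yes | yes |
| Parent Self-Efficacy Scale | Primary | yes | yes |
| Attitudes questionnaire | Primary | yes | yes |
| Student Social Behavior Questionnaire | Primary | yes | yes |
| Intention | Primary | no | yes |
| Acceptability Survey | Secondary | no | yes |

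Five of the six primary measures are taken twice. Of the seven quantitative measures, two are post-only. The open-ended qualitative questions are left out of this count.

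**3. Planned records, N = 40.**

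- Measured twice: 40 × 2 = 80 per score.
- Intention, item by item: 40 × 1 = 40 per item.
- Intention, four items jointly: 40 × 4 = 160 ratings, all post-training.

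**4. What the model can estimate.** In its linear form, for parent i in school j at time t:

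y = μ + β·time + school(j) + parent(i) + error

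- For intention, time takes one value for every record. It cannot be separated from μ, so β is not estimable. This holds for 40 records or for 160.
- With one record per parent and item, the parent effect cannot be separated from the error. In a joint model of the four items it can be, but β still cannot.
- A mean and a school effect remain estimable.

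**5. Precision of the school effect.** Section 4.3 gives, as a reason for using three schools, that the study will "estimate the random effect for school for powering our future proposals involving multiple schools". Three schools leave 3 − 1 = 2 degrees of freedom. A 95% chi-square interval for a mean square on 2 df runs from 2/7.378 = 0.27 to 2/0.0506 = 39.5 times the estimate. This is an interval for the between-school mean square, not for the variance component itself. The limit applies to every outcome. It matters here only because a post-only model with a school effect is an option in the fix.

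**The case against.** The strongest reply is that both faults are slips of wording. The stem sits in a summary, and the real form may be correct. Even if it was fielded, the outcome's name, the prospective verb and the timing straight after training all push parents towards the future reading, and nothing shows that they would answer about past use. On the analysis, the post-only timing is clear from Sections 3.1.1.2, 4.1.a and 4.2 and from the opening of the last paragraph of Section 4.3. That paragraph already plans descriptive summaries. The model sentence begins with the aim of finding changes, so it can be read as limited to outcomes where change is measured. The plan will also use AICc to drop random effects that are not needed.

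Part of this stands. The effect of the stem on the data cannot be sized, and the text does not prove that a change analysis of intention is intended. The consequence is modest.

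The rest does not remove the point. The description needs correcting whichever way the form reads. The clearer passages show the inconsistency but do not correct the outcome definition in Section 4.3, which is where an analyst will look. AICc can remove a random effect; it cannot create a time effect from one measurement. A reading of the definition that exempts intention from the list of changes is grammatically possible but strained.

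**Conclusion.** The concern holds. The stem contradicts itself as printed, and Section 4.3 defines success on intention as a change that the design cannot estimate. This affects one of six primary measures, with four ratings per parent and 40 parents planned. The model sentence also reaches the post-only acceptability survey. The five primary measures with a baseline, the sample size and the power statement are not touched.

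The contradiction in the stem and the absence of a baseline are certain from the text. Harm to the intention data depends on the form carrying the same stem, which the documents do not show. A false claim of improvement depends on a literal reading of Section 4.3, which its own wording permits.

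**What to change.** 1. Check the survey form. If it carries this stem, use one prospective window, such as the next month, in both the form and Section 4.2. If the form is sound, correct Section 4.2 only.
2. If data were already collected with this stem (Section 2.8 gives first enrollment as 4/2/2022), report the exact wording and interpret the ratings cautiously, as descriptive.
3. In the outcome definition in Section 4.3, take intention out of the list of changes and name it as a post-training level, consistent with Section 4.1.a.
4. In the model sentence, limit the time effect and the repeated-observations model to outcomes measured at both time points.
5. Summarise intention and acceptability with the planned means, SDs and percentages, and claim no change. A post-only model that keeps the school effect may be added, with its imprecision stated.
6. State whether the four intention ratings are analysed item by item or jointly.

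The cost is very low: one check of the form, one corrected description and edits to two sentences of Section 4.3. IRB review is needed if the form changes (Section 3.1.2.1). Sample size, visits, the descriptive analyses and the school-level estimate are all kept.

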**Type**

Secondary

**Name**

Acceptability Survey

**Time Frame**

Immediate post-assessment

**Brief Description:**

An 8-item questionnaire measuring user-friendliness, utility, and relevance of the Parent Module

**Type**

Secondary

**Name**

Qualitative questions

**Time Frame**

Immediate post-assessment

**Brief Description:**

Brief open-end questions that ask how helpful the program was, how the liked program was, and whether the user has any suggested changes to the program.

### 4.3 Statistical Analysis Plan

Analyses will be conducted on data collected. While unlikely, data may not be missing at random (NMAR). [name], Project Biostatistician, will assign all lost responses to extreme category and perform multiple imputation procedures that can handle various amounts of missing data and use covariates and propensity scores.

The primary outcomes are detecting positive changes in knowledge acquisition and confidence, attitudes about bullying, self-efficacy regarding bullying, and intention to use of the STAC parent strategies. The secondary outcomes are program acceptability. A total of 20 parents within one school provides at least 80% power to detect a difference in baseline and immediate follow-up corresponding to a medium effect size (e.g., Cohen's  $d = .5$ ) with a 5% type I error probability. For this power analysis, pilot data from a sample of teachers were analyzed using measures similar to those proposed in this study. We will use three schools to ensure ecological validity and estimate the random effect for school for powering our future proposals involving multiple schools. We propose planning for 40 parents.

Descriptive statistics will be used to initially characterize the outcomes. We will use linear or generalized linear mixed model framework, with random effects of repeated observations on parents and parents nested within school.

We will evaluate whether the STAC Parent Module increases knowledge and confidence, changes attitudes about bullying, and increases self-efficacy from baseline to immediate follow-up, as well as intention to use the STAC parent strategies at the immediate follow-up. We will also evaluate acceptability at the immediate follow-up. Means, SDs, and percentages will be used to describe the primary and secondary outcomes. To identify changes in outcomes, we will evaluate each outcome using analysis of variance in a linear or generalized linear mixed model framework, with random effects of repeated observations on parents and parents nested in school. We will address the appropriateness of the model for non-normal outcomes and apply the appropriate distribution as necessary, and we will assess models for the necessity of all random effects using Akaike information criterion (AICC). As the proposed project is intended to test feasibility and short-term outcomes to provide data for a larger multi-site study, we do not propose testing of moderators. However, we will examine demographic variables as a fixed effect whenever possible. Because our focus is on reception and usability, we will not perform a counterfactual analysis, but will have preliminary data to power for this in future proposals. Qualitative summary reports will also be prepared.

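### The missing-data rule in section 4.3 gives neither the extreme-category fill nor multiple imputation a role, and leaves the extreme end undefined

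*Combined protocol and SAP*

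**What the plan says.** Section 4.3 opens with "Analyses will be conducted on data collected", and continues: "While unlikely, data may not be missing at random (NMAR"). It then says that the project biostatistician "will assign all lost responses to extreme category and perform multiple imputation procedures that can handle various amounts of missing data". The only detail given on how the imputation would work is that it will "use covariates and propensity scores". Nothing more is said on missing values. The model description later in 4.3 does not mention filled or imputed data, and section 3.3 only aims to keep missing data low.

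No missing rate is given. Sections 3.1.1.4 and 3.1.2.2 let parents decline any question. Sections 2.5.2 and 3.1.1.2 describe one session of about 1.5 hours, with baseline survey, training and post survey in sequence.

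The outcomes in section 4.2 range from long questionnaires (10, 11 and 13 items) to short sets. One component of a primary measure is "confidence about managing bullying behavior (3 items on a 5-point likert scale"; another primary measure includes this component: "A 6-item scale measures parent communication self-efficacy in talking to adolescents about bullying". Intention to use the strategies (primary) and acceptability (secondary) are measured only after training.

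**The concern.** The rule permits three analysis data sets (observed, filled, imputed) and ties none of them to the mixed model. Taken literally, once every lost response has been placed in an extreme category there is nothing left to impute. The result is a single deterministic imputation that treats invented values as observed. The study has one group (section 4.1.e), so no control arm can offset a one-directional shift.

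The direction is open too. A worst-case fill and a best-case fill both fit the wording, and they push results in opposite directions. Two analysts following section 4.3 could report different estimates from the same surveys. Those estimates are meant to help power later proposals, so a shift would carry forward.

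**Working it through.** The plan gives no figure on missing data to reproduce. Its only calculated figure, power with 20 parents, does not bear on this point.

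**Inputs.** From the documents: N = 40, an effect of d = 0.5, 5% type I error (all section 4.3), and the item counts in section 4.2. Assumed, because the documents do not give them: scores on 1-5, pre-post correlation r = 0.5, SD of 0.5, 0.8 or 1.0, baseline mean of 3.1 or 3.5, loss at random, a two-sided paired t-test with benefit counted in the upper tail. With r = 0.5 the standardized change is 0.5/√(2 × (1 − 0.5)) = 0.5, and power with no loss is about 87%.

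**Post-only outcome.** Shift in mean = (m/N) × (endpoint − observed mean). With m = 2 and an assumed observed mean of 3.5:
- top fill: 2/40 × (5 − 3.5) = +0.075
- bottom fill: 2/40 × (1 − 3.5) = −0.125

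If 80% of the 38 respondents answer favourably, the reported percentage becomes (38 × 0.8 + 2)/40 = 81% or (38 × 0.8)/40 = 76%.

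**Pre-post scale, one item skipped at post only.** A parent who skips one of K items gets the score ((K − 1) × own mean + endpoint)/K, taking the skipped item as otherwise equal to the parent's own mean. Mean change is then true change + (m/N) × (1/K) × (endpoint − post mean). Example with SD 0.8, baseline 3.5, true change 0.4 (post mean 3.9), m = 4, K = 3:
- bottom: 0.4 + 0.1 × (1/3) × (1 − 3.9) = 0.303, or 0.38 SD
- top: 0.4 + 0.1 × (1/3) × (5 − 3.9) = 0.437, or 0.55 SD

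The true value is 0.50 SD. Simulated power over the assumed SDs and baseline means (at least 20,000 runs each):

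| Items in scale | Parents skipping, post only | Bottom fill | Top fill |
|---|---|---|---|
| 3 | 4 of 40 | 39-71% | 91-96% |
| 6 | 4 of 40 | 69-81% | 89-93% |
| 10 | 4 of 40 | 78-84% | 89-91% |
| 13 | 4 of 40 | 81-85% | 88-90% |

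On the 3-item set, bottom fill gives 78-84% with one skip and 66-80% with two. With no true change and four post-only skips on that set, top fill declares benefit in 5-10% of runs, against a nominal 2.5%.

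**Skipping equal at baseline and post.** The endpoint now enters both means and cancels, leaving true change × (1 − m/(N × K)). For m = 4 and K = 3 that is 0.5 × (1 − 4/120) = 0.48 SD. Simulated power on the 3-item set is 86-87% with either fill if the same parents skip both times, and 70-86% if different parents skip. On 10 items it is 85-87%. False benefit is not inflated in any of these cases.

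**Size of an imputation model.** Items measured twice: 11 + (4 + 3 + 4) + (6 + 6) + 10 + 13 = 57. Adding the 4 intention and 8 acceptability items gives 57 × 2 + 4 + 8 = 126 item variables for 40 parents, so one joint item-level model is not practical.

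**The case against.** The sequence in section 4.3 (data collected, then NMAR as an unlikely event, then the methods) can fairly be read as observed-data primary with the fill as a check on NMAR. On that reading only a label is missing. This stands as the probable intent. It does not settle the rule, which assigns all lost responses without a condition and never calls this a sensitivity analysis.

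Three stronger readings are tempting, and the documents do not support them.

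- *A reader might infer that the fill will distort the main results.* The large figures need skipping after training but not before, and nothing in the documents points to that pattern. They also need four parents to skip within one 3-item set, which section 4.2 does not say is scored alone. A parent who declines an uncomfortable question may well decline it twice, and then the fill has almost no effect on change.
- *A reader might infer that the direction is a special problem for the attitude measures.* Section 4.1.a lists "increases in knowledge and confidence, changes in bullying attitudes, increases in self-efficacy to manage bullying" and section 4.3 likewise speaks only of a change in attitudes ("increases knowledge and confidence, changes attitudes about bullying, and increases self-efficacy from baseline to immediate follow-up"). But the outcome statement in 4.3 includes attitudes among the changes hoped to be positive, and section 4.2 gives no scoring direction for the knowledge, comfort and confidence, or self-efficacy measures either. The definition is missing for all of them.
- *A reader might infer that observed-data analysis is safe.* The runs assume loss at random. If data were truly NMAR, the observed-data result would be biased too, which is a reason to keep a sensitivity analysis.

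It is also fair that this is a single-session pilot of 40 parents, where loss of whole post surveys is unlikely.

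**Conclusion.** The gap is real: the only missing-data rule names two methods, gives neither a role, and leaves the fill without a direction, level or time point. Followed literally, it replaces missing answers with fixed extreme values and makes the imputation empty.

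The consequence is certain in kind for post-only outcomes and conditional for pre-post change. It can be material on a very short scale with unbalanced skipping. With balanced skipping the bias is close to nil, and the cost is mainly added variance on very short scales. On 10- to 13-item scales the effect is small. All sizes rest on assumed means, SDs, correlation and missing counts, so they illustrate and do not predict. Confidence is high on the ambiguity and low on the size. Severity is minor to should-fix.

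**What to change.** In section 4.3:

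1. State that the primary analysis is the planned mixed model on observed data, with no extreme-category fill.
2. Use multiple imputation, if at all, under MAR for partly answered scales, with a short variable list fixed in advance.
3. Keep extreme-category assignment only as a labelled NMAR sensitivity analysis, run in both the best and the worst direction, with both results reported.
4. For every instrument, define the favourable end, whether the assignment works on items or scale scores, and whether it applies at baseline, post or both.
5. Report intention and acceptability on observed data, with the number missing.

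The cost is SAP wording and two short extra sensitivity runs. No new data are needed.

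### Does the power statement for 20 parents in one school need correcting because it cannot be reproduced and gives no figure for the 40 parents planned?

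*Combined protocol and SAP*

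**What the plan says.** Section 4.3 holds the only power statement: "A total of 20 parents within one school provides at least 80% power to detect a difference in baseline and immediate follow-up", for a medium effect (Cohen's d of 0.5) at a 5% type I error. The basis follows directly: "For this power analysis, pilot data from a sample of teachers were analyzed using measures similar to those proposed in this study". Three schools are to be used for ecological validity and to "estimate the random effect for school for powering our future proposals involving multiple schools". The paragraph then closes on the sample size: "We propose planning for 40 parents".

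On analysis, the same section says: "To identify changes in outcomes, we will evaluate each outcome using analysis of variance in a linear or generalized linear mixed model framework". Parent and school enter that model as random terms. Intention to use the strategies is to be evaluated "as well as intention to use the STAC parent strategies at the immediate follow-up" only.

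Section 4.2 lists five primary instruments measured at baseline and immediately after training. Some hold more than one score. The National Education Association survey has a comfort scale as well as "confidence about managing bullying behavior (3 items on a 5-point likert scale), and role in managing bullying behavior". The Parent Self-Efficacy Scale has one part on helping the adolescent respond, and for the other: "A 6-item scale measures parent communication self-efficacy in talking to adolescents about bullying".

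**The concern.** A pre-post power figure depends on how d is standardised. A d of 0.5 in SDs of the change is a different effect from a d of 0.5 in raw-score SDs, and the two are linked by the pre-post correlation. The plan gives neither the definition nor the correlation, and it does not name the test or its sidedness. On the reading many statisticians would try first (paired t, d in SDs of the change, two-sided), 20 parents fall well short of 80%, so the sentence looks wrong.

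It also describes 20 parents in one school, while the analysis is a mixed model over 40 parents in three schools, and no power or detectable change is given for 40. Nor does it say which of at least eight pre-post scores it covers: PAPPS as one, three in the National Education Association survey, two in the Parent Self-Efficacy Scale, and one each in the two attitude questionnaires. The intention items have no baseline, so a pre-post calculation cannot apply to them.

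If the claim were false and 40 rested on it, the pilot might be too small for its primary outcomes, and the error could carry into the later proposals it is meant to inform.

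**Working it through.** **Inputs from section 4.3:** n = 20; d = 0.5; type I error 5%; power at least 80%; planned n = 40. **Not given, so varied here:** sidedness, standardiser, pre-post correlation ρ.

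**Formula.** For a paired comparison, power comes from the noncentral t distribution with n − 1 degrees of freedom and noncentrality dz·√n, where dz is the mean change divided by the SD of the change.

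**1. The plan's figure, with d in SDs of the change (dz = 0.5).**

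| n | Noncentrality | Two-sided 5% | One-sided 5% |
|---|---|---|---|
| 20 | 0.5·√20 = 2.24 | 56.5% | 69.5% |
| 27 | 0.5·√27 = 2.60 | – | 81.2% |
| 34 | 0.5·√34 = 2.92 | 80.8% | 88.7% |
| 40 | 0.5·√40 = 3.16 | 86.9% | 92.8% |

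The stated 80% is not reproduced at n = 20. It would take 34 parents two-sided or 27 one-sided.

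**2. The plan's figure, with d in raw-score SDs.** With equal SDs before and after, dz = 0.5/√(2(1 − ρ)). At n = 20, 80% power needs dz = 0.660 two-sided, which gives ρ = 1 − 0.5·(0.5/0.660)² = 0.71. One-sided it needs dz = 0.577, which gives ρ = 0.62. So the stated figure can be reached.

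| ρ (assumed) | dz | Power, n = 20 | Power, n = 40 | n for 80% |
|---|---|---|---|---|
| 0.3 | 0.423 | 43% | 74% | 46 |
| 0.4 | 0.456 | 49% | 80% | 40 |
| 0.5 | 0.500 | 56% | 87% | 34 |
| 0.6 | 0.559 | 66% | 93% | 28 |
| 0.7 | 0.645 | 78% | 98% | 21 |
| 0.8 | 0.791 | 92% | >99% | 15 |

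(All two-sided 5%, per outcome, no multiplicity adjustment.)

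**3. How firm the 0.71 is.** It assumes equal SDs. If d uses the baseline SD and the post SD is k times it, the variance of the change is 1 + k² − 2ρk in baseline units. Setting 0.5/√(1 + k² − 2ρk) = 0.660 gives ρ = 0.67 for k = 0.8 and ρ = 0.78 for k = 1.2. One-sided, the values are 0.56 and 0.70. So 0.71 is not a pass mark for the claim.

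**4. What matters for the study: n = 40.** The smallest change detectable with 80% power two-sided is 0.454 SD of the change. On the raw-score reading with equal SDs, 40 parents reach 80% once ρ is at least 1 − 0.5·(0.5/0.454)² = 0.39. If the sponsor's claim for 20 is true two-sided (ρ of about 0.71), power at 40 is about 98%.

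**5. Mixed model against paired t.** With complete, approximately normal data, a parent random intercept and no school-level variation in change, the test of time in the planned model is the paired t: a school intercept common to both occasions cancels from the difference. In five simulated data sets (40 parents, three schools, two occasions) the two statistics agreed to within 0.0001.

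**The case for a change.** The strongest case for a change is that this is the plan's only quantitative support for its sample size, that a reader cannot tell 56% from 80%, and that one sentence would settle it. Teachers are not parents and the pilot measures were only similar, so a correlation carried over from them is an assumption and ought to be stated. The study is also meant to inform later power calculations, where the same ambiguity moves the two-sided n for 80% from 46 (ρ = 0.3) to 15 (ρ = 0.8).

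The description of the gap stands: the inputs are missing, and stating them would be good practice. What does not follow is that anything in this study would go differently. The 56% applies only under a definition of d that the plan never adopts. Rewriting the sentence around that definition would replace the sponsor's pilot-based calculation with a reviewer's guess. Section 2.8 gives first enrolment as 4/2/2022, so if recruitment has begun, a new figure would be retrospective. A later proposal will need its own calculation, and this study will give the analysts the SD of the change in parents directly, which is better evidence than a correlation quoted from teachers.

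The silence about 40 is also less serious than it looks. The paragraph can be read as saying that 20 suffice for the pre-post change and that more parents, over three schools, serve ecological validity and estimation of the school effect. Unless change varies appreciably between schools, 40 parents do no worse than 20.

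**Conclusion.** No change follows. The figure of at least 80% for 20 parents cannot be reproduced from the text, but it is attainable on an ordinary reading (raw-score d, pre-post correlation of about 0.71 two-sided or 0.62 one-sided with equal SDs), and the plan names a data source that could have supplied the correlation. The 40 parents are not shown to be too few: 87% two-sided for 0.5 SD of the change, about 98% if the sponsor's own claim holds, and below 80% only on the raw-score reading with a correlation under about 0.39.

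These figures assume complete, approximately normal data, a two-sided 5% test per outcome, and no school-level variation in change, for which the documents give no value. They apply to the pre-post scores. The post-only intention items are to be described by means, SDs and percentages and do not depend on the power sentence.

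This is a reporting gap in a single-group pilot. The analysis does not use the power figure, and anyone reading the results will have the observed changes and SDs.
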